#### Comparisons of Several Groups

All continuous data (non-normally distributed) with several dependent groups (Baseline, 12th month, 1. Year) will be compared by Friedman's test.

Normally distributed continuous data with several dependent groups (Baseline, 12th month, 1. Year) will be compared by Repeated Measures ANOVA test.

Continuous, normally distributed data with several independent groups will be compared by ANOVA test. For statistically significant results, Post Hoc comparisons will be done with Tukey HSD test.

Continuous, non-normally distributed data with several independent groups will be compared by Kruskal-Wallis test. For statistically significant results, Post Hoc comparisons will be done with Mann Whitney u test.

#### **9.4.3.2 Statistical Methods by Evaluation of Study Objective**

##### **Primary Objective:**

Primary objective of the study will be evaluated by the statistical methods which are stated below:

- Calculated scores of BICAMS (SDMT, CVLT2 and BVMTR) at baseline, 12th month and 24th month will be compared by using Repeated Measures ANOVA (if variables are non-normally distributed Friedman Test).

Post-Hoc comparisons will be done with Tukey test. (if Friedman test was used, Wilcoxon Signed Rank test will be used for Post-Hoc comparisons.)

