### **2.3 Primary and secondary endpoints:**

#### **2.3.1 Primary endpoint:**

- To evaluate the effects of Fingolimod on cognitive performance in highly active relapsing remitting multiple sclerosis patients comparing baseline, month 12 and month 24, as assessed by BICAMS battery test.

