## 6.4 Efficacy

### 6.4.1 Cognitive Tests

The Brief International Cognitive Assessment for Multiple Sclerosis (BICAMS) Battery test is the primary efficacy assessment criteria. Cognitive tests will be performed to RRMS patients at baseline and at months 6, 12 and 24 at the study center.

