### **9.4 Analysis of Efficacy Variables**

#### **9.4.1 Primary efficacy endpoint:**

The primary end-point was planned as evaluating the effects of Fingolimod on cognitive performance in highly active, RRMS patients comparing cognitive performance at baseline and at Month 24, after treatment for two years as assessed by BICAMS battery test.

In this study, it is proposed to observe an increase of 3 points in SDMT testing (which roughly equals to 5 % increase in SDMT overall score) is meaningful and in our study, with treatment we may expect a 5% increase in cognitive functioning during a considerably longer duration of treatment and follow-up.

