### **9.4.3 Statistical model, hypothesis, and method of analysis**

The basic hypothesis of the study is improvements in cognitive tests in RRMS patients. The sample size calculation for the study has been based on an improvement with treatment in a cognitive test (SDMT).

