#### **9.4.3.1 Data analysis**

##### **General Approach**

All Statistical analyses will be performed with MedCalc Statistical Software version 13.1.2 (MedCalc Software bvba, Ostend, Belgium; <http://www.medcalc.org>; 2014) at the 5% significance level using 2-sided tests or 2-sided Confidence Intervals.

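### The primary comparison is stated in two ways (baseline against Month 24, and a three-visit test), and three BICAMS scores are each tested at 5% with no rule for success

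*Combined protocol and SAP*

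**What the plan says.** **Visits.** Section 9.4.1 defines the primary endpoint as "comparing cognitive performance at baseline and at Month 24, after treatment for two years as assessed by BICAMS battery test", and section 9.6 repeats this. Section 2.3.1 defines it as "comparing baseline, month 12 and month 24, as assessed by BICAMS battery test". Section 9.4.3.2 follows 2.3.1 and compares the three visits by repeated measures ANOVA, or by Friedman's test if the data are non-normal.

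**Follow-up tests.** After the ANOVA, "Post-Hoc comparisons will be done with Tukey test". On the other branch, "if Friedman test was used, Wilcoxon Signed Rank test will be used for Post-Hoc comparisons". Month 24 against baseline is one of three pairs in either case.

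**Scores.** Section 6.4.1 states: "The Brief International Cognitive Assessment for Multiple Sclerosis (BICAMS) Battery test is the primary efficacy assessment criteria". Section 9.4.3.2 lists the data to be compared as "Calculated scores of BICAMS (SDMT, CVLT2 and BVMTR) at baseline" and the two later visits, and defines no composite. The General Approach in 9.4.3.1 sets all tests "at the 5% significance level using 2-sided tests or 2-sided Confidence Intervals".

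**The role of SDMT.** Section 9.4.3 states: "The sample size calculation for the study has been based on an improvement with treatment in a cognitive test (SDMT". Section 9.6 postulates a 5% SDMT improvement at 24 months, and section 9.4.1, under the primary endpoint heading, calls a 3-point SDMT rise meaningful. No section names SDMT as the primary score or makes 3 points a criterion for success.

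**The concern.** The three-visit test and the Month 24 contrast answer different questions. The first asks whether the mean differs at any visit. It has no direction, although section 9.4.3 hypothesises improvement, and a change at Month 12 alone can make it significant. The plan does not say which result decides.

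The scores raise the same difficulty. With three tests at 5% and no any-of-three or all-three rule, the error rate of the primary conclusion is undefined. The deciding score and visit could be settled after results are known. The study is open-label, and sections 3.4 and 9.7 allow yearly interim analyses, so Month 12 results may be seen early. Without a control arm, prespecification is one of the few protections left.

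**Working it through.** **1. Does the sample size settle which comparison is primary?** Section 9.6 gives 73 patients, alpha 0.05, a 5% improvement and no power. It states no formula. A precision formula for a single proportion reproduces the figure:

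n = z² p(1 − p)/d² = 1.960² × 0.05 × 0.95 / 0.05² = 72.99, so 73.

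The match is inferred from the number alone. The enrolment figure follows approximately: 73 × 1.1 = 80.3, and 80 are enrolled. This formula fits neither a paired Month 24 contrast nor a three-visit ANOVA, so the sizing does not decide between them.

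**2. Inputs for the error rates.** From the documents: n = 73, three visits, three scores, two-sided 5%, and an SDMT change of 3 points. The documents give no SD or correlation, so these are assumed. Three cases, with SD of change = SD × √(2(1 − r)):

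| Case | SD | Visit correlation r | SD of change |
|---|---|---|---|
| A | 12 | 0.5 | 12.0 |
| B | 10 | 0.7 | 7.75 |
| C | 8 | 0.8 | 5.06 |

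The figures below come from 20,000 simulated trials per setting with normal data and equal correlations between visits. Power for the paired t test is from the noncentral t distribution.

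**3. Three scores, no true change.** If the scores were independent, the chance that at least one is significant is 1 − 0.95³ = 14.3%. In simulation it is 11–14% for correlations between scores of 0.7 down to 0. The chance that all three are significant is under 1%. An all-three rule errs most often when two scores truly change and the third does not. Its error is then bounded by the 5% level of the remaining test, and simulation gives about 5%.

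**4. Two definitions of the visits, one score.**

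| Mean at baseline / Month 12 / Month 24 | Result | A | B | C |
|---|---|---|---|---|
| 0 / 1.5 / 3 (steady) | three-visit test significant | 45% | 84% | 99.6% |
| | Month 24 paired t significant | 56% | 90% | 99.9% |
| | the two disagree | about 15% | about 8% | about 0.2% |
| 0 / 3 / 0 (gain lost) | three-visit test significant | 59% | 93% | 99.98% |
| | significant while Month 24 is not | 54% | 88% | 95% |

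Under steady change the Month 24 contrast has more power than the three-visit test, so designating it loses nothing there. A steady 3-point decline makes the three-visit test significant as often as a rise does (about 46–99.7%). That test alone cannot establish improvement.

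**5. Pairs within one score, no true change.** Tukey with the within-subject error term controls the three visit pairs on the ANOVA branch. For the Wilcoxon pairs, the chance of at least one false positive is about 12–13% if they are always run and about 4% if they are run only after a significant Friedman test.

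**The case against.** **SDMT is already the lead score in substance.** It is the only score in the sizing rationale, and 9.4.1 gives its 3-point change under the primary endpoint heading. This stands as a strong implication. It is not a designation, because 6.4.1 makes the whole battery primary and 9.4.3.2 treats the three scores alike.

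**The two visit definitions overlap.** Month 24 against baseline is among the planned pairs. In the gain-lost case Tukey flags that pair in only about 2% of trials, so a full report would show that the gain had gone. This also stands. What is missing is a statement that this pair decides.

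**The large disagreement is a worst case.** A reader might infer from 54–95% that the two definitions usually conflict. The documents do not support that: they postulate improvement at 24 months, and under steady change disagreement is 0.2–15%.

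**The Wilcoxon step may be gated.** A reader might infer that the Friedman branch runs at 12–13%. Post-hoc testing ordinarily follows a significant overall test, and 9.4.3.1 states that convention for independent groups. On that reading the figure is about 4%. The gap is that the gate is not written for dependent groups.

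**The study is single-arm, open-label and Phase IV, with no stated power.** This lowers the severity. It does not remove the point, because the plan states a hypothesis, a primary endpoint and a significance level.

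**Conclusion.** The concern holds in measured form. Sections 9.4.1 and 9.6 contradict sections 2.3.1 and 9.4.3.2 on the primary comparison, and no rule turns three scores tested at 5% into one conclusion. Both facts are read directly from the text.

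The sizes depend on the assumed SDs of 8–12 and visit correlations of 0.5–0.8, and on which rule is applied. A reader might infer that the plan's primary error rate is 14%. That would require any single score to count as success, which the plan does not say. Nor does it call for all three, under which the error would be at most about 5%. The defect is that the rate is undefined.

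This should be fixed before any analysis. Given the design and the absence of a power claim, it does not by itself invalidate the study.

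**What to change.** Amend the protocol before any analysis, including any yearly interim:

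- Name one primary test: SDMT change from baseline to Month 24, paired t test, two-sided 5%, with the signed-rank test as a sensitivity analysis. Claim improvement only if the change is positive. Section 9.4.3.1 already lists the paired t test.
- Make CVLT2, BVMTR, the three-visit tests and all Month 12 comparisons secondary.
- If the sponsor prefers to keep all three scores primary, test the same Month 24 contrast on each. Use Holm if any one score may count, or state that all three must be significant at 5% each.
- Reconcile 2.3.1, 6.4.1, 9.4.1, 9.4.3.2 and 9.6, including the wording that makes the whole BICAMS battery primary.
- State that Wilcoxon pairs are run only after a significant Friedman test.
- Editorial, in 9.4.3.1: signed-rank is for two dependent, non-normal samples, and the visits are baseline, Month 12 and Month 24.

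**Cost.** Section 11.1 requires a written amendment approved by the sponsor, the IRB/IEC and, where required, health authorities. No new data or visits are needed. CVLT2 and BVMTR lose co-primary status, and a change seen only at Month 12 no longer counts as primary. Under Holm, SDMT may have to pass at 0.05/3 = 1.67%. Power for +3 points at n = 73 is then 38–99.5% instead of 56–99.9% over cases A to C. Holding 80% power at that level needs ((2.394 + 0.842)/(1.960 + 0.842))² = 1.33 times the patients, and holding 90% needs 1.29 times.

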##### **Secondary Objectives:**

Secondary objectives of the study will be evaluated by the statistical methods which are stated below:

- The effect of fingolimod on biomarkers (24OHC, Osteopontin and Metalloproteinase) at months 6, 12, 24 will be evaluated by comparing the levels of biomarkers. The evaluation among time points will be made by using Repeated Measures ANOVA.
- The effect of fingolimod on brain gray matter atrophy and thalamic atrophy will be evaluated by comparing MRI parameters at baseline, 6th, 12th, 24th months.

The comparison among time points will be made by Repeated Measures ANOVA. (if variables are non-normally distributed Friedman Test).

- Investigation the effect of fingolimod on cognitive performance in highly active relapsing remitting multiple sclerosis patients comparing baseline, 12th and 24th month, as assessed by PASAT and Stroop test will be made by Repeated Measures ANOVA. (if variables are non-normally distributed Friedman Test).
- Correlation between cognitive performance and MRI data will be calculated by using Pearson Correlation Coefficient (or Spearman Correlation Coefficient) between PASAT, STROOP and BICAMS tests scores and MRI parameters.

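### Repeated Measures ANOVA is specified with no sphericity check or correction, so its 5% level and the pooled-error Tukey contrasts for the primary endpoint hold only under an untested covariance assumption

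*Combined protocol and SAP*

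**What the plan says.** - **Error rate.** Section 9.4.3.1 (General Approach) runs all analyses "at the 5% significance level using 2-sided tests or 2-sided Confidence Intervals".
- **General rule.** Section 9.4.3.1 (Comparisons of Several Groups) says normally distributed repeated data "will be compared by Repeated Measures ANOVA test". Non-normal data take another route: "All continuous data (non-normally distributed) with several dependent groups (Baseline, 12th month, 1. Year) will be compared by Friedman's test".
- **Primary.** The endpoint in Section 2.3.1 is stated as "comparing baseline, month 12 and month 24, as assessed by BICAMS battery test", so there are three visits. Section 9.4.3.2 says the scores "will be compared by using Repeated Measures ANOVA (if variables are non-normally distributed Friedman Test", with Tukey as the post-hoc step after the ANOVA. Sections 9.4.1 and 9.6 describe the primary endpoint as month 24 against baseline.
- **Secondary.** For MRI the plan is "comparing MRI parameters at baseline, 6 th , 12 th , 24 th months", so there are four visits: "The comparison among time points will be made by Repeated Measures ANOVA", or Friedman if non-normal. PASAT and Stroop use three visits and the same pair of methods. For biomarkers, "The evaluation among time points will be made by using Repeated Measures ANOVA", with months 6, 12 and 24 listed.
- **Assumption checks.** Shapiro-Wilk for normality is the only one named. Sphericity, an epsilon correction, a multivariate test and an unstructured-covariance model are not mentioned, and Section 9.4.4 lists no supportive analyses.

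**The concern.** The uncorrected F test has its nominal level only if the differences between every pair of visits have the same variance. There are reasons to doubt that here. Baseline is measured before the first dose and the later visits on drug. The MRI visits are unequally spaced at 0, 6, 12 and 24 months. Patients may also change at different rates, or their scores may correlate less as visits move apart; in either case the 0–24 month difference is the most variable one.

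Two things are at stake. The omnibus test then uses too many degrees of freedom and rejects too often. Separately, the single pooled error behind Tukey averages over all intervals, so it is too small for the longest one. That longest interval is the contrast Sections 9.4.1 and 9.6 put at the centre of the trial.

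**Working it through.** **Inputs.** Level 5% two-sided (9.4.3.1); k = 3 visits for BICAMS and k = 4 for MRI (9.4.3.2); n = 73 (9.6). The documents give no visit SDs, correlations or epsilon (ε), so every covariance below is an assumption.

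**1. The plan's own figure.** Box's approximation to the true level of the uncorrected test is

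α(ε) = P[ F(ε(k−1), ε(k−1)(n−1)) > F₀.₉₅(k−1, (k−1)(n−1)) ].

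At ε = 1 this returns exactly 5.00%, the stated level.

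**2. Upper bounds.** The smallest possible ε is 1/(k−1).
- Three visits, ε = 1/2: F₀.₉₅(2, 144) = 3.059, and P[F(1, 72) > 3.059] = 8.5%.
- Four visits, ε = 1/3: F₀.₉₅(3, 216) = 2.646, and P[F(1, 72) > 2.646] = 10.8%.

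**3. One worked epsilon.** Take three yearly visits, unit variances and correlation 0.8 per year, so 0.64 over two years. Double-centring the covariance matrix gives diagonal 0.204, 0.098, 0.204 and off-diagonals −0.049, −0.156, −0.049. Then ε = (trace)² / [2 × sum of squares] = 0.5067² / (2 × 0.1511) = 0.85, and α = P[F(1.70, 122.3) > 3.059] = 5.9%.

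**4. Simulated level with no true change** (n = 73, 40,000 trials per row, Monte Carlo SE about 0.1 point; GG = Greenhouse-Geisser).

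| Assumed covariance | 3 visits: ε | uncorrected | GG | 4 visits: ε | uncorrected | GG |
|---|---|---|---|---|---|---|
| Compound symmetry | 1.00 | 5.2% | 5.0% | 1.00 | 5.0% | 4.7% |
| Decay, 0.5 per year | 0.93 | 5.5% | 5.0% | 0.79 | 6.3% | 4.9% |
| Decay, 0.8 per year | 0.85 | 5.9% | 5.0% | 0.69 | 7.0% | 5.0% |
| Decay, 0.95 per year | 0.81 | 6.1% | 5.0% | 0.65 | 7.3% | 5.1% |
| Decay 0.8 plus 25% independent error | 0.96 | 5.3% | 5.0% | 0.91 | 5.5% | 4.8% |
| Slopes, SD ratio 0.5 | 0.96 | 5.4% | 5.0% | 0.96 | 5.2% | 4.7% |
| Slopes, SD ratio 1 | 0.80 | 6.0% | 4.9% | 0.74 | 6.7% | 4.9% |
| Slopes, SD ratio 2 | 0.61 | 7.4% | 4.9% | 0.47 | 9.0% | 5.0% |
| Slopes, SD ratio 3 | 0.55 | 7.8% | 5.0% | 0.40 | 9.7% | 5.0% |

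The SD ratio is the yearly slope SD divided by the measurement-error SD.

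**5. Pooled error for the primary contrast.** The pooled variance of a difference is the average of all pairwise difference variances. Its ratio to the true variance of month 24 minus baseline has a closed form for three yearly visits.
- Decay with yearly correlation r: (3 + r) / [3(1 + r)]. For r = 0.5: 3.5/4.5 = 0.778, square root 0.88, so the SE is 12% too small. For r = 0.95: 3.95/5.85 = 0.675, square root 0.82, so 18% too small.
- Slopes with SD ratio s: the pairwise variances are 2 + s², 2 + s² and 2 + 4s², which average 2 + 2s². The ratio is (1 + s²)/(1 + 2s²). For s = 0.5: 1.25/1.5 = 0.833, square root 0.91, so 9% too small. For s = 3: 10/19 = 0.526, square root 0.73, so 27% too small.

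For baseline to month 12 the direction reverses. With s = 1 the pooled variance is 4 against a true 3; the square root of 4/3 is 1.15, so that SE is about 15% too large.

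**6. Tukey for month 24 versus baseline alone**, by simulation at three visits: the false-positive rate is 1.8% under compound symmetry, 3.9–5.2% under decay (0.5–0.95) and about 9% with slope SD ratio 3.

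**The case against.** The case for leaving the text alone has several sound parts.

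- **Not every repeated comparison is affected.** Non-normal variables go to Friedman by the general rule. Only the biomarker bullet omits that fallback, and the general rule still covers it.
- **The covariance is unknown.** A reader might infer that the true level is 6–7% for three visits and 7–10% for four. The documents do not support that as fact. Mild slopes, or decay with independent error, give only about 5.3–5.5% for three visits, and values near 10% for four need slope SD about three times error SD. Section 9.4.2 measures volumes cross-sectionally at each visit; stable between-patient differences plus independent error would be close to compound symmetry, where nothing is lost.
- **The four-visit figures belong to MRI only.** Biomarkers are sampled four times, but Section 9.4.3.2 lists months 6, 12 and 24, and Section 2.3.2 lists baseline, month 12 and month 24. No four-visit biomarker test is specified.
- **Pooled-error contrasts are planned only for the primary.** No post-hoc test is named for MRI or biomarkers. A baseline-to-month-24 comparison of two paired samples falls under the paired t test in Section 9.4.3.1, which has no sphericity condition.
- **The stakes are limited.** This is a single-arm, open-label study sized without regard to power.

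All of this narrows the point. None of it supplies a sphericity check or correction, and none of it repairs the Tukey step. The software might print a corrected p-value, but the plan does not say which one would be reported, and that should not be left open until the data are seen.

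**Conclusion.** The point holds in conditional form. For normally distributed variables the 5% omnibus level depends on sphericity, which the plan neither checks nor corrects for and which this design makes doubtful. Under the assumed covariances at n = 73, the level is near 5% if sphericity roughly holds. With decaying correlation it is 5.3–6.1% for three visits. For the four MRI visits it is 6.3–7.3%, or 5.5% when substantial independent error is added. The ceilings of about 8.5% and 10.8% do not depend on a scenario.

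The more consequential part is the primary post-hoc contrast. If Tukey is applied in its standard pooled form, the SE for month 24 versus baseline is 9–27% too small in the decay and slope scenarios, and any interval built on it is too narrow.

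It would be wrong to infer that the bias always favours finding a change. At ε = 1 there is none, and short-interval contrasts can be conservative. The inflation is modest, but it touches the primary analysis and is easily avoided, so the text should be changed.

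**What to change.** In Sections 9.4.3.1 and 9.4.3.2:

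1. Wherever Repeated Measures ANOVA is named, specify Greenhouse-Geisser corrected degrees of freedom, or a repeated-measures model with unstructured covariance, and state that this is the p-value to be reported.
2. For the primary, replace the Tukey step with paired comparisons that use each difference's own standard error, with a Bonferroni or Holm adjustment. The adjustment is needed because dropping Tukey removes the only between-visit multiplicity control after the primary ANOVA; two unadjusted visit-versus-baseline tests at 5% would allow up to about 10% familywise error. Bonferroni would test each at 0.05/2 = 2.5% for two comparisons, or 0.05/3 = 1.7% for all three.

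This is a wording change with no new data. The cost is a very small loss of power if sphericity holds: under compound symmetry the corrected test ran at 5.0% against 5.2% (three visits) and 4.7% against 5.0% (four visits).

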##### **Secondary Objectives:**

Secondary objectives of the study will be evaluated by the statistical methods which are stated below:

- The effect of fingolimod on biomarkers (24OHC, Osteopontin and Metalloproteinase) at months 6, 12, 24 will be evaluated by comparing the levels of biomarkers. The evaluation among time points will be made by using Repeated Measures ANOVA.
- The effect of fingolimod on brain gray matter atrophy and thalamic atrophy will be evaluated by comparing MRI parameters at baseline, 6th, 12th, 24th months.

The comparison among time points will be made by Repeated Measures ANOVA. (if variables are non-normally distributed Friedman Test).

- Investigation the effect of fingolimod on cognitive performance in highly active relapsing remitting multiple sclerosis patients comparing baseline, 12th and 24th month, as assessed by PASAT and Stroop test will be made by Repeated Measures ANOVA. (if variables are non-normally distributed Friedman Test).
- Correlation between cognitive performance and MRI data will be calculated by using Pearson Correlation Coefficient (or Spearman Correlation Coefficient) between PASAT, STROOP and BICAMS tests scores and MRI parameters.

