#### **2.3.2 Secondary endpoints:**

-To measure the difference in serum levels of 24S-hydroxycholesterol (24OHC) , osteopontin and matrix metalloproteinases (and also MMPI's) between baseline and after fingolimod treatment at month 12 and month 24.

-To evaluate the effect of fingolimod on cognitive performance in highly active relapsing remitting multiple sclerosis patients comparing baseline, month 12 and month 24, as assessed by PASAT and Stroop test.

-To evaluate the effect of fingolimod on brain gray matter atrophy and thalamic atrophy by comparing MRI data between baseline and month 24.

-To evaluate the correlation between effect of fingolimod on cognitive performances and brain atrophy (gray matter atrophy and thalamic atrophy) by comparing baseline and month 24.

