### **3 Investigational plan**

#### **3.1 Study design**

This is a 24-month, open-label, multicenter study with a single treatment arm design.

80 relapsing-remitting MS (RRMS) patients according to the McDonald criteria will be recruited in the study. All subjects will sign an informed consent that will be approved by the Ethics Committee.

Upon signing the informed consent, patients will enter a screening phase to be evaluated for eligibility. Screening visit will take place during month -1 to 0. Eligible patients will be given the study drug at baseline visit (Visit 1) and these patients will enter the 24-month open-label treatment phase.

At screening period, patient's eligibility criteria will be confirmed. Patients, who will be monitored at the site, will receive their first doses at the clinic, be observed during the 6-hour monitoring period.

Serum samples will be collected from each participant after evaluation for inclusion and exclusion criteria at baseline and at months 6, 12 and 24 for measurement of 24 hydroxy cholesterol, osteopontin and matrix metalloproteinases (including MMP1's).

BICAMS Battery will be used in this study. The Brief International Cognitive Assessment for MS (BICAMS) includes 3 cognitive tests, Symbol Digit Modalities Test (SDMT, the second edition of the California Verbal Learning Test (CVLT2) and the revised Brief Visuospatial Memory Test (BVMTR). BICAMS Battery will be performed to RRMS patients at baseline and at months 6, 12 and 24.

PASAT will be performed at baseline and at months 6, 12 and 24.

[figure not shown]
Stroop test will be performed at baseline and at months 6, 12 and 24.

Beck Depression Inventory-II will be performed to distinguish depression and cognitive impairment.

MRI scans will be obtained at baseline and at months 6, 12, 18 and 24 by using 1.5T MRI for measuring gray matter atrophy and thalamic atrophy ( a standard scanning protocol will be used for MRI in all centers).

EDSS will be recorded at baseline and at months 3, 6, 12, 18 and 24.

**Figure 1:** Study protocol flow-chart

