### **6.4.3 Biomarkers**

Serum samples will be collected at baseline and at months 6, 12 and 24 from each participant after evaluation for inclusion and exclusion criteria for measurement of 24 hydroxy cholesterol, osteopontin and matrix metalloproteinases (including MMP1's).

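### The biomarker ANOVA lists Months 6, 12 and 24 but omits baseline, so as written it does not test the biomarker endpoint

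*Combined protocol and SAP*

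**What the plan says.** - **Endpoint (Section 2.3.2).** The biomarker endpoint is the difference in serum levels "between baseline and after fingolimod treatment at month 12 and month 24".
- **Analysis (Section 9.4.3.2, Secondary Objectives).** "The effect of fingolimod on biomarkers (24OHC, Osteopontin and Metalloproteinase) at months 6, 12, 24 will be evaluated by comparing the levels of biomarkers". The next sentence assigns Repeated Measures ANOVA across time points. Baseline is not mentioned, and no contrast is named.
- **Sampling (Section 6.4.3, also Section 3.1 and Table 6-1).** "Serum samples will be collected at baseline and at months 6, 12 and 24 from each participant".
- **Neighbouring items in Section 9.4.3.2.** The MRI item starts from baseline: "The effect of fingolimod on brain gray matter atrophy and thalamic atrophy will be evaluated by comparing MRI parameters at baseline". The BICAMS and PASAT/Stroop items also name baseline.
- **General rule (Section 9.4.3.1, Comparisons of Several Groups).** Non-normal data "with several dependent groups (Baseline, 12th month, 1. Year) will be compared by Friedman's test", and the Repeated Measures ANOVA rule carries the same list of visits.
- **Design (Section 3.1).** "This is a 24-month, open-label, multicenter study with a single treatment arm design".
- **Correlation analysis.** Section 9.4.3.2 correlates values "between PASAT, STROOP and BICAMS tests scores and MRI parameters" without naming a visit or a change variable. Section 2.3.2 refers to "brain atrophy (gray matter atrophy and thalamic atrophy) by comparing baseline and month 24".

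**The concern.** The endpoint needs baseline, Month 12 and Month 24. The listed analysis has Months 6, 12 and 24. With no control arm, baseline is the only untreated reference in the study, and it is the level left out.

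An ANOVA on the three on-treatment visits tests whether their means are equal. A biomarker that moved by Month 6 and then held steady satisfies that null hypothesis exactly, so a real change from baseline would go undetected. Conversely, a significant result would show that on-treatment visits differ from each other, which is not the difference that Section 2.3.2 asks about.

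A secondary gap of the same kind is that the correlation item does not carry over the baseline and Month 24 definition in Section 2.3.2. That is missing detail, not a contradiction.

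**Working it through.** **Step 1: compare the visit lists.**

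| Source | Visits |
|---|---|
| Biomarker endpoint, 2.3.2 | Baseline, 12, 24 |
| Biomarker sampling, 3.1, 6.4.3, Table 6-1 | Baseline, 6, 12, 24 |
| Biomarker analysis, 9.4.3.2 | 6, 12, 24 |
| MRI analysis, 9.4.3.2 | Baseline, 6, 12, 24 |
| BICAMS and PASAT/Stroop analyses, 9.4.3.2 | Baseline, 12, 24 |
| General rule, 9.4.3.1 | Baseline, 12th month, 1st year |

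Biomarkers are the only repeated-measures item in 9.4.3.2 without baseline. The general rule supports reading this as a slip because it does name baseline. It cannot supply the missing list, because it gives Month 12 twice (12th month and 1st year) and has neither Month 6 nor Month 24. The post-hoc rule in 9.4.3.2 sits under the primary objective, so no biomarker contrast against baseline is specified anywhere.

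**Step 2: inputs for the consequence.** The plan states no power figure for biomarkers, so there is none to reproduce. From the plan: two-sided 5% level (9.4.3.1); 80 enrolled with 10% loss (9.6), giving 80 × 0.90 = 72. Assumed, because the documents give no biomarker SD, effect or time course: SD 1, equal correlation ρ of 0.5, 0.7 or 0.8 between visits, and a total shift of 0.2, 0.3 or 0.5 SD. Three time courses at Months 6/12/24, as fractions of the total: early and sustained 1/1/1; Month 12 plateau 0.5/1/1; linear 0.25/0.5/1.

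**Step 3: formula.** Power comes from the noncentral F distribution with λ = n·Σ(μ − mean μ)²/(1 − ρ), on k − 1 and (n − 1)(k − 1) degrees of freedom.

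Worked case, 0.3 SD, early shift, ρ = 0.5:
- With baseline: means 0, 0.3, 0.3, 0.3; average 0.225; sum of squares 0.0675; λ = 72 × 0.0675/0.5 = 9.72 on 3 and 213 df; power 0.739.
- Without baseline: all three means are equal, so λ = 0 and the rejection rate is 0.050.

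**Step 4: results** (range over ρ = 0.5 to 0.8).

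| Total shift | Time course | Without baseline | With baseline |
|---|---|---|---|
| 0.2 SD | Early, sustained | 5% | 38–79% |
| 0.2 SD | Month 12 plateau | 13–26% | 35–75% |
| 0.2 SD | Linear | 19–43% | 28–64% |
| 0.3 SD | Early, sustained | 5% | 74–99% |
| 0.3 SD | Month 12 plateau | 24–53% | 70–98% |
| 0.3 SD | Linear | 39–78% | 59–95% |
| 0.5 SD | Early, sustained | 5% | over 99% |
| 0.5 SD | Month 12 plateau | 57–94% | 99–100% |
| 0.5 SD | Linear | 83–100% | 97–100% |

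The 0.3 SD cells were checked against 20,000 simulated trials each and agree within 0.007.

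**Step 5: the contrast itself.** For a paired t test of Month 24 against baseline, the noncentrality is 0.3·√72/√(2(1 − ρ)). This gives 2.55, 3.29 and 4.02 at ρ = 0.5, 0.7 and 0.8, and power of 71%, 90% and 98%. All three time courses end at the same Month 24 shift, so these values hold for each.

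**Step 6: the correlation.** By Fisher's z, the correlation detectable with 80% power at n = 72 is tanh((1.960 + 0.842)/√69) = 0.325.

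**The case against.** The strongest reply is that baseline is implied. The months in the biomarker item can be read as the visits at which an effect is assessed. In a single-arm study an effect at Month 6 can only mean change from baseline. The endpoint says so, the sample is taken, the general rule names baseline, and a paired t test is available in 9.4.3.1. An analyst with all this in hand would probably include baseline. That is fair, and the omission is most likely unintended. But no section makes baseline a level of the biomarker ANOVA or assigns the paired test to biomarkers. Because the sibling items all name baseline, its absence here could be taken as deliberate.

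The power figures rest on assumptions, and the range of ρ matters. At ρ = 0.3 and a 0.3 SD shift, power with baseline falls to 58% (early) and 44% (linear), and the paired t test to 56%. The lower ends in the table are therefore not floors. The 5% for an early sustained shift does not depend on these choices, since equal means reject at the significance level. For a large gradual change the loss is small.

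Adding baseline while keeping Month 6 still leaves an overall test that differs from Section 2.3.2; only the named contrasts match the endpoint. Naming two contrasts for each of several biomarkers also raises multiplicity, which the plan should address. Neither point is a reason to leave baseline out.

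**Conclusion.** The concern holds. The only section that specifies the biomarker analysis omits the reference visit on which the endpoint is defined, and no other section repairs it. As written, the ANOVA would answer a different question from the endpoint. It would have no power beyond 5% for an early sustained shift, with a loss under the other two time courses that shrinks as the change becomes larger and more gradual. Those magnitudes assume 72 evaluable patients, equal correlation between visits and the shift sizes shown; the direction of the problem needs none of these. The point affects secondary endpoints only. The primary analysis and the sample size are unchanged.

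**What to change.** 1. In Section 9.4.3.2, give the biomarker time points as baseline and Months 6, 12 and 24. Name Month 12 against baseline and Month 24 against baseline as the contrasts that answer Section 2.3.2, and say whether they are adjusted for multiplicity or treated as descriptive.
2. In Section 9.4.3.1 (Comparisons of Several Groups), correct the visit list to baseline, Month 12 and Month 24, adding Month 6 where Section 9.4.3.2 uses it.
3. As a supporting clarification, define the correlation as the baseline-to-Month-24 change in each PASAT, Stroop and BICAMS score against the baseline-to-Month-24 change in gray matter and thalamic volume.

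**Cost.** Items 1 and 2 are wording only, since every sample is already in Table 6-1. The extra level can cost the overall test a little power if all change occurs between Months 12 and 24. The worst case checked was 39.3% without baseline against 37.9% with it, at 0.2 SD and ρ = 0.5. Item 3 has a real price: change scores are noisier and need both visits, and each volume change is a difference between two cross-sectional measurements (Section 9.4.2). At n = 72, a true correlation below about 0.33 has less than 80% power.
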